# **Hypothesis 1:**

Those randomized to AHA's Depression Screen, Notify & Treat intervention group will gain significantly more quality-adjusted life years across 18 months when compared to No Depression Screen control group, and also when compared to the Depression Screen & Notify control group.

We will compare outcomes for participants randomized to each of the three groups. Change in QALYs from baseline through 18 months post-randomization will serve as the primary outcome for this trial. First, quality of life utilities will be calculated using participants' scores on the SF-12 at each visit (baseline [pre-randomization] and 6, 12,

and 18 months post-randomization). All participants who complete the SF-12 will be classified according to the SF-6D. The SF-6D describes 18,000 health states. The average profile for each randomized group will be calculated. A multiple regression formula that applies weights will be used to assign quality of life utilities for each participant. Next, QALYs will be derived by multiplying the SF-6D derived quality of life utilities by 0.5 years for each 6 month-period, assuming linearity for changes in utility within each period. Any mortality events will be assigned zero QALYs from that point to the end of follow-up. With these scores calculated, we will calculate the average QALY gained (or lost) in each randomized group compared to assuming the utility calculated at baseline remained constant across 18-months.

The goal of the primary analysis is to identify whether there is difference in QALYs among the three groups. We plan to perform a two-step gate-keeping test procedure: We will first perform an F-test using ANOVA, and then proceed to do all three pairwise comparisons using two-sided t-test at 5% nominal significance *only if* the F-test has a p-value less than 0.05. With three randomization groups and three pairwise comparisons, this two-step procedure has been shown to preserve the familywise error rate in the strong sense, that is, a false positive comparison will occur at most with 5% probability under all possible scenarios.  This method is also generally more powerful than Bonferroni's adjustments.

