5.3 Primary Efficacy Analysis

Change in QALYs from baseline through 18 months post-randomization will serve as the primary outcome for this trial. QALYs were chosen as the primary outcome to facilitate comparisons of the effect of depression screening with other preventive interventions as well as to facilitate cost-effectiveness analyses and policy decisions. As QALYs do not directly assess depression, this outcome measure also minimized possible patient reporting bias as a result of lack of participant blinding or masking to condition. The goal of the primary analysis is to identify whether there is difference in the change in QALYs among the three groups. QALYs describe the duration of illness per years of survival, adjusted for quality of life experienced during that survival. One year in perfect health is equivalent to 1 QALY. All patients will complete a standardized measure of quality of life using the Short Form-12 Health Survey, Version 2™ (SF-12) at baseline, and again at 6-months, 12-months, and 18-months. 1 QALYs will be estimated from the SF-12 using the Short Form 6 Duration (SF6D) which converts data from 7 items in the SF-12 assessing 6 domains (physical functioning, role limitations, social functioning, pain, mental health and vitality) to QALYs.2 Study patients who die during the study period will be assigned a utility score of 0 for assessments after the date of death. QALYs over 18 months will be calculated as the area-under-curve by interpolating linearly the scores at the four assessments (baseline, 6-month, 12-month, 18-month). There were no data obtained or available for these measures between assessments. Change in QALYs will then be obtained by subtracting the QALYs that would have occurred if there was no change in the baseline utility score from the actual QALYs that were measured across 18 months. The analysis will follow the principle of intention-to-treat and will be conducted on each imputed dataset with the point

estimate deriving from the average of 5 datasets and the pooled variance calculated using Rubin's formula.

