5.6 Missing Data

CESD-10 questionnaire with missing data will be prorated if that participant answered more than 7 items. The missingness of data will then be assessed using Little's test. If data are found to missing at random, we will perform multivariated imputations to generate 5 imputed datasets by basing on covariates which were predictive of missing pattern such as input from prior visit and site variable; random sampling was used to impute the missing values at baseline. Missing data will be imputed sequentially, starting with the baseline visit, then the 6-month visit, followed by the 12-month and 18-month visits.

In sensitivity analyses, missing data will be handled by carrying the last observed value forward and by using best case-worst case scenario – in best case, we assumed that all missing had perfect health. In worst case scenario, we assumed all missing data had worst health status (QOL = 0).

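### The best-case and worst-case fills in SAP 5.6 do not exclude baseline, so their labels reverse for patients with a missing baseline utility; the primary analysis is unaffected

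*SAP*

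**What the plan says.** SAP 5.3 builds the primary endpoint in two steps. First, "QALYs over 18 months will be calculated as the area-under-curve by interpolating linearly the scores at the four assessments". Second, the change is obtained by "subtracting the QALYs that would have occurred if there was no change in the baseline utility score from the actual QALYs" measured. The protocol (Statistical Methods, Hypothesis 1) uses the same reference, with the gain or loss "compared to assuming the utility calculated at baseline remained constant across 18-months".

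SAP 5.6 describes multiple imputation for the main analysis, working forward from the baseline visit, and notes that "random sampling was used to impute the missing values at baseline". It then lists three sensitivity methods: last observed value carried forward, a best case in which "in best case, we assumed that all missing had perfect health", and a worst case in which "we assumed all missing data had worst health status (QOL = 0"). No visit is exempted from any of the three.

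**The concern.** A best-case fill should push a patient's result up and a worst-case fill should push it down. That holds for follow-up utilities, which enter the endpoint with positive weights. It fails for baseline, which sets the level that is subtracted: a patient given perfect health at baseline can only stay level or decline, and one given 0 can only stay level or improve. Baseline also has the largest absolute weight of the four visits.

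Last observation carried forward has a related gap, since nothing precedes baseline to be carried and SAP 5.6 names no fallback. At stake is how the sensitivity analyses are read. In patients without a baseline, the two scenarios work against the fills applied to missing follow-up, so the spread between scenarios is narrower than the labels suggest.

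**Working it through.** **Inputs.** Visits at 0, 6, 12 and 18 months, with linear interpolation and baseline subtraction (SAP 5.3). Perfect health is scored 1, since "One year in perfect health is equivalent to 1 QALY". The worst-case value is 0 (SAP 5.6). The planned difference is 0.031 QALY, with 500 per arm after 5% loss (SAP 5.4). Follow-up utility is not given: 0.75 is assumed, with a range of 0.6 to 0.9. The share of missing baselines is not given: 1% to 2% per arm is assumed for illustration.

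**The plan's own yardstick.** SAP 5.4 states no figure for these scenarios, but its design difference reproduces: 0.21 × 0.2 + 0.055 × 0.8 = 0.086, and 0.086 - 0.055 = 0.031. With SD 0.17, two-sided 5% and 80% power, the usual formula gives 473 per group against the stated 475.

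**Endpoint weights.** Write u0, u6, u12 and u18 for the utilities.

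- Area under the curve: 0.25·u0 + 0.5·u6 + 0.5·u12 + 0.25·u18
- Baseline held constant: 1.5·u0
- Change: -1.25·u0 + 0.5·u6 + 0.5·u12 + 0.25·u18

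The weights sum to 0.

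**Best case minus worst case, by pattern.** The fills differ by 1, so the gap for a patient is the sum of the weights of the missing visits.

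| Visits missing | Best minus worst (QALY) |
|---|---|
| 18 months only | +0.25 |
| All follow-up, baseline observed | +1.25 |
| Baseline only | -1.25 |
| Baseline and 18 months | -1.00 |
| Baseline and either 6 or 12 months | -0.75 |
| Baseline, 18 months, and either 6 or 12 months | -0.50 |
| Baseline, 6 and 12 months | -0.25 |
| All four | 0 |

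Every pattern that includes baseline is reversed, except the last, where both scenarios give exactly 0.

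**One patient missing only baseline, follow-up utility 0.75.**

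- Best case: 1.25 × 0.75 - 1.25 × 1 = -0.3125
- Worst case: 1.25 × 0.75 - 1.25 × 0 = +0.9375

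Over assumed utilities of 0.6 to 0.9, the best case runs from -0.50 to -0.125 and the worst case from +0.75 to +1.125.

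**Mean of one arm.** If a share q of the arm lacks only baseline, its best-case mean is 1.25·q below its worst-case mean from those patients: 0.0125 at 1% and 0.025 at 2%. The gap equals 0.031 at q = 0.031/1.25 = 2.48%.

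**Difference between arms.** Baseline is due before allocation, so the expected imbalance in missing baselines is zero. Treat the counts in two arms as independent with mean m each; their difference has SD √(2m). Taking +0.9375 as each patient's displacement in the worst case:

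- 1% per arm (m = 5): √10 × 0.9375/500 = 0.006
- 2% per arm (m = 10): √20 × 0.9375/500 = 0.008

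**The case against.** The strongest reply is that the situation should hardly arise. The protocol (Implementation) and SAP 3 both place randomization after all baseline assessments are complete, and the SF-12 is a baseline form. SAP 5.6 also does not say which baseline values were missing; it opens with the CESD-10, so they could be CESD-10 items or covariates. Since carrying a value forward makes sense only after baseline, one could read the whole sensitivity paragraph as covering follow-up alone.

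Much of this limits the size, and that part stands. It does not remove the defect. The follow-up-only reading needs a restriction that SAP 5.6 does not contain. SAP 5.3 runs the QALY analysis on the imputed datasets, and the imputation starts at baseline, so a missing baseline utility is provided for. Completing a visit does not exclude skipped items either: the utility uses seven SF-12 items, and SAP 5.6 gives a proration rule only for the CESD-10.

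A reader might also infer a large bias in the treatment comparison. If 10 of 500 patients in one arm and none in another lacked baseline, the worst case would move the difference by 10/500 × 0.9375 = 0.019, about 60% of 0.031. The documents do not support that as a typical size. Missingness before allocation cannot be caused by allocation, and if 10 such patients fell across two equal arms, the chance that all fell in one named arm would be 0.5^10, about 0.001.

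Nor do the documents say that the scenarios bound the treatment difference. Both give every arm the same fill, so even for follow-up data they describe the level of change and not the extremes of a contrast.

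**Conclusion.** The rule is wrong as written, in a narrow place. The sign follows from the SAP's own definitions and needs no outside figure: a baseline filled with 1 lowers the endpoint and one filled with 0 raises it. The labels are correct whenever baseline is observed.

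The practical size cannot be fixed from the documents because no count of missing baselines is given; it is probably small. The arm-level gap of 0.0125 QALY per 1% missing only baseline does not depend on the assumed follow-up utility. The chance shifts in the arm difference, roughly 0.006 to 0.008 QALY (one SD), rest on the assumed utility of 0.75 and on 1% to 2% missing per arm.

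A reader should not conclude that the primary result is at risk. The multiple-imputation analysis, the two-step test procedure and the sample size do not use these fills.

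**What to change.** In SAP 5.6, state that the perfect-health fill, the zero fill and last observation carried forward apply to post-baseline visits only. A missing baseline keeps the values imputed for the primary analysis. Those values differ between the five datasets, so each scenario should be run in all five and pooled with Rubin's formula, as SAP 5.3 already does for the main result. The text should add that when the 6-month value is missing too, the value carried forward is the imputed baseline.

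Swapping the two fills at baseline would also make the labels match the endpoint. It would keep extreme values at a visit that precedes randomization, so the restriction is preferable.

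The cost is a sentence or two in the SAP and a rerun of the sensitivity analyses on datasets that already exist. No new data are needed, and the primary analysis does not change. Reporting the number of missing baseline utilities by arm would let readers judge how much the point matters.

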6. BASELINE CHARACTERISTICS

Baseline characteristics will be examined as means (standard deviation) or percentages by randomization assignment to assess for a balanced allocation.

7. SAFETY/ TOLERABILITY

7.1 Primary (pre-specified) Safety Outcomes

Harms attributable to use of antidepressant medications (i.e., appetite problems, sleep problems, gastrointestinal upset, and bleeding) will be assessed through patient interview. Group differences in the prevalence of these potential adverse effects will be compared using chi-squared tests.

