who are randomized to the AHA Depression Screen, Notify & Treat arm will also complete a PHQ-8 assessment, and those with clinically significant scores (≥ 10) will be offered the option of receiving treatment for their depressive symptoms. Participants will be presented with the option of receiving medication therapy (sertraline or bupropion), Cognitive Behavioral Therapy (delivered via phone), a combination of both therapies or neither therapy. Depending on their treatment choice, they will be scheduled for their initial treatment visit, ideally within two weeks of randomization. Their PCP and/or cardiologists will also be notified if they have clinically significant scores (≥ 10) on the PHQ-8 assessment. Those randomized to No Depression Screen group will not receive the depression screen PHQ-8 at baseline.

All participants, regardless of randomization assignment, will complete the CES-D10, SF-12 health-related quality of life measure, symptoms checklist and lost productivity at enrollment and after 6-, 12-, and 18-months of study participation. All participants will also complete the PHQ-8 assessment at 18-months, with referral to treatment for those with scores ≥ 10. Participants will be contacted by telephone, or have an in-person visit scheduled, as they prefer. These administration methods have been compared in past studies and found to be equivalent. These follow-up contacts will be brief, and scheduled at the participant's convenience wherever possible.

All participants will report their health service utilization at 6-, 12- and 18-months. Additionally, all will have EMR searches of health care utilization extracted for the 18-month duration of the trial.

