#### **Blinding**

The blinded coordinator (BC) will administer all study regular assessments at 6-, 12- and 18-months, and will not be allowed to know the participants' group allocation, and this is ensured by the "user-role" designation in the tracking system. In addition to the UC, and due to the nature of the study treatment, participants, site PIs, and other personnel not designated as BC, cannot be blinded to the group allocation, but are encouraged not to disclose the allocation either at or when assisting the BC in scheduling follow up assessments. After each study visit, the BC will complete a 1-item questionnaire asking if the participant disclosed if they were in treatment. This information will be tracked, however no intervention will occur if the BC becomes unblinded.

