# **Procedures for Side Effects Due to Study Antidepressants:**

Participants will have all possible side-effects carefully described and explained before any course of anti-depressants is initiated. Site medication providers have undergone thorough training on the detection and management of side-effects with [name], who remains available for consultation with the site medication prescribers. Below is an overview of what was taught, and will be followed for the trial:

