The blinded coordinator (BC) will administer all study regular assessments at 6-, 12- and 18-months, and will not be allowed to know the participants' group allocation, and this is ensured by the "user-role" designation in the tracking system. In addition to the UC, and due to the nature of the study treatment, participants, site Pls, and other personnel not designated as BC, cannot be blinded to the group allocation, but are encouraged not to disclose the allocation either at or when assisting the BC in scheduling follow up assessments. After each study visit, the BC will complete a 1-item questionnaire asking if the participant disclosed if they were in treatment. This information will be tracked, however no intervention will occur if the BC becomes unblinded.

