The other prespecified secondary outcome will be Health Care Costs and Lost Productivity. 1 At baseline, 6-months, 12-months, and 18-months, patients will report measures of economic productivity, including employment status, occupation, hours spent at work, and time lost from work for health-related reasons.11 At 6-months, 12-months, and 18-months, patients will also report healthcare utilization since their last intake assessment, including emergency department (ED) visits, hospitalizations (location, admission and discharge dates), psychiatric medication use, name and dose, ambulatory care visits with mental health specialists, cardiologists, as well as PCPs and finally hospitalizations for cardiovascular events. Patient self-reports of healthcare utilization will be supplemented by review of the EMR and claims systems to collect data on healthcare utilization during the 18-month trial period. Average Medicare reimbursement rates according to diagnosis-related groups will be applied to inpatient visits to estimate hospitalization costs, and the Medicare physician fee schedule will be applied to outpatient and ED resource use according to current procedural terminology codes. Costs of study depression treatment will also be incorporated into estimates of healthcare utilization costs for those assigned to the Screen, Notify, and Treat group who agree to depression treatment by study personnel. To estimate economic costs from a societal perspective, changes in productivity and time spent traveling to appointments will also be accounted for. Costs will be standardized across years using the U.S. Consumer Price Index and presented in U.S. dollars.12

-

¹Cost of health care utilization was erroneously listed as a co-primary outcome on the initial clinicaltrials.gov entry. This error was corrected in clinicaltrials.gov on October 25, 2017, prior to completion of data collection or any interim data analyses. As can be seen in the planned statistical analyses, the sample size for the study was driven entirely by the change in QALYs outcome. Cost-effectiveness analyses, in contrast, were never intended to be listed as a co-primary outcome as they were not guided by economic hypotheses involving statistical tests and sample size calculations for incremental cost-effectiveness ratios were never attempted.

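### Bleeding is a pre-specified harm measured only by interview of unblinded participants; inpatient and ED records extracted in every arm are not used beside it, or to compare hospitalisation for safety

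*SAP*

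**What the plan says.** SAP 7.1 defines the pre-specified safety outcomes as appetite problems, sleep problems, gastrointestinal upset and bleeding. The only source it names is in the words "and bleeding) will be assessed through patient interview". The analysis is equally short: "Group differences in the prevalence of these potential adverse effects will be compared using chi-squared tests".

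On blinding, the Protocol (Blinding) says that "participants, site PIs, and other personnel not designated as BC, cannot be blinded to the group allocation", and SAP 3 repeats this. The interviewer is masked: "The blinded coordinator (BC) will administer all study regular assessments at 6-, 12- and 18-months". Under the Protocol's procedures for side effects of study antidepressants, "Participants will have all possible side-effects carefully described and explained before any course of anti-depressants is initiated".

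On records, the Protocol (Interventions) says that "all will have EMR searches of health care utilization extracted for the 18-month duration of the trial". The cost overview in the Outcomes section shows that this covers ED and urgent care, inpatient, outpatient and diagnostic services. SAP 8 also has patients report, among other items, "ambulatory care visits with mental health specialists, cardiologists, as well as PCPs and finally hospitalizations for cardiovascular events", supplemented by the EMR and claims systems. All of this sits under costs. SAP 7.2 takes mortality from patient surrogates and the EMR, and compares it between groups.

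**The concern.** Bleeding differs from the other three harms because its serious form brings people to an ED or a hospital bed, where it is recorded whatever the participant later recalls or attributes to treatment. The plan nevertheless relies on recall by people who know their allocation.

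SAP 5.3 recognises this kind of bias for efficacy: it defends the choice of QALYs partly because they are less open to reporting bias in unblinded patients. SAP 7.1 has no counterpart for harms.

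The plan also makes no between-arm safety comparison of cardiovascular or all-cause hospitalisation. These data are being collected in a post-ACS population in which, according to the Protocol's background, comorbid depression carries a two-fold higher risk of recurrent ACS and death.

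What is at stake is the interpretation of the harms table. An excess of reported bleeding in Screen, Notify & Treat could not be attributed with confidence. The absence of an excess would say little about serious bleeding. No primary result or decision rule is affected.

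**Working it through.** **The plan's own figures.** The documents contain no power or precision calculation for harms. The only sample-size calculation is for QALYs: 475 per group, and 475 / 0.95 = 500 after 5% loss. It reproduces, and it matters here only as the denominator.

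**Step 1. Sources side by side.**

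| Item | Source in the plan | Compared between arms for safety? |
|---|---|---|
| Appetite, sleep, GI upset, bleeding (SAP 7.1) | Interview | Yes, chi-squared |
| Mortality (SAP 7.2) | Surrogates and EMR | Yes, chi-squared |
| Hospitalisation and ED use (SAP 8) | Self-report, EMR, claims | No, costs only |
| Adverse event reports (Protocol, Harms) | Site investigator to IRB and DSMB | No analysis in the SAP |

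**Step 2. Who has had side effects explained.** SAP 5.4 expects 20% of the Screen, Notify & Treat arm to screen positive: 0.20 × 500 = 100 people. They may choose medication, therapy, both or neither, and uptake is not stated. Assuming 25% to 100% take medication gives 25 to 100 people in one arm.

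**Step 3. Size of a reporting artefact.** Let u be medication uptake and e the extra reporting among medicated people (assumed 10 to 30 points). The whole-arm excess is d = 0.20 × u × e.
- Low end: 0.20 × 0.25 × 0.10 = 0.5 points.
- High end: 0.20 × 1.0 × 0.30 = 6.0 points.

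The chance that this artefact alone gives p < 0.05 in one pairwise comparison, with n = 475 per arm, background rate p and q = p + d, is approximately Φ(z − 1.96) + Φ(−z − 1.96), where z = d / √{[p(1−p) + q(1−q)] / n}.

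| Whole-arm excess d | p = 5% | p = 20% |
|---|---|---|
| 0.5 points | 6% | 5% |
| 2.0 points | about 25% | about 12% |
| 6.0 points | 93% | 60% |

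A false signal is likely only if uptake and over-reporting are both high.

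**Step 4. Artefact and harm look the same.** Take 50 medicated people and an assumed 10% background. If reporting rises to 20% in those 50, there are 50 × 0.10 = 5 extra reports, and 5 / 500 = 1.0 point. If the drug truly doubles bleeding in the same 50, the result is again 1.0 point. The formula above gives about 8% power for 10% against 11%. So the problem is that the result cannot be interpreted, more than that a false positive is likely.

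**Step 5. The same test applied to the records.** Use 500 per arm, since extraction covers all participants, and the same true doubling in 50 people. Assume a background of 1% to 5% for inpatient or ED bleeding over 18 months.
- Extra events: 50 × 0.01 = 0.5 to 50 × 0.05 = 2.5, which is 0.1 to 0.5 points of the arm.
- 95% CI half-width: 1.96 × √[2p(1−p) / 500] = 1.2 points at 1% and 2.7 points at 5%.
- Power by the formula above is about 5% to 6%.
- An observed excess would have to reach about 0.0123 × 500 = 6 events (at 1%) or 0.027 × 500 = 14 events (at 5%) before the interval excluded zero.

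Records can therefore flag or bound a large excess of serious bleeding. They cannot decide whether a small interview excess is real.

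**The case against.** The strongest reply is that the plan has safeguards and that the added analysis is weak.

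- **Safeguards.** The Protocol gives a symptoms checklist to all arms at baseline, 6, 12 and 18 months. This is presumably the interview that SAP 7.1 means, though neither document says so. The follow-up interviewer is blinded. Investigators record adverse events, suspected serious reactions have expedited reporting, and the DSMB meets twice a year. A reader might infer that serious harm goes unmonitored; the documents do not support that. But none of these steps removes over-reporting by an unblinded participant, SAP 7.1 does not mention baseline values, and the SAP plans no between-arm analysis of the adverse event reports.
- **Reach of the counselling.** A reader might infer that interviewed patients in general were primed. The passage concerns only people about to start an antidepressant, at most about 100 of 500 in one arm. Control patients treated by their own clinicians may hear similar advice.
- **Neutrality of the records.** A reader might call the extract arm-neutral. It is obtained the same way in all arms, but provider notification and study contacts differ by arm and may change visits, detection or coding. Inpatient and ED events are probably less exposed. The extract is described for costing, and no bleeding code list is given.
- **Precision.** Step 5 shows that the records comparison would be imprecise. This stands, and it rules out presenting the addition as decisive.
- **Hospitalisation as a separate preference.** In what the Protocol calls a screening trial, mortality is already compared. Adding hospitalisation corrects no error in SAP 7.1. It does use data already collected on serious events in this population.

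**Conclusion.** The point holds in a limited form. Bleeding rests on interview of unblinded participants alone, and the inpatient and ED extract is not used to corroborate it or to compare hospitalisation for safety, although the EMR already supports the mortality comparison. Under the assumed ranges, an artefact would add 0.5 to 6.0 points to one arm, and the interview data alone cannot separate it from a real harm of the same size.

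Two stronger readings are tempting and should be resisted. One is that all four harms should come from records: appetite, sleep and mild gastrointestinal symptoms are naturally self-reported and would not be captured reliably. The other is that records would settle whether an interview excess is real: 0.1 to 0.5 points against a half-width of 1.2 to 2.7 points says otherwise.

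Medication uptake, extra reporting and all background rates are assumptions, since the documents give none. Only the 20% screen-positive share and the arm sizes come from the plan. This is a worthwhile, inexpensive improvement to safety reporting, not a flaw in the trial's main inference.

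**What to change.** In SAP 7.1, keep the interview outcomes for all four harms and state which form supplies them. Beside the bleeding item, add inpatient or ED encounters with a bleeding diagnosis in the 18-month extract, identified masked to allocation by a code list fixed before unblinding. First confirm that diagnosis fields are in the extract; the documents name reimbursement groups and procedure codes for costing.

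In SAP 7.2, add by-arm counts of cardiovascular and all-cause hospitalisation from the same extract. Report all additions descriptively, as risk differences with 95% CIs and no further tests. If unblinding has already occurred, label them post hoc.

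State the limits in the SAP:
- Counts will be low and intervals wide, so only a large excess of serious events can be flagged or bounded.
- Encounters outside the participating systems are missed.
- Notification and study contacts may affect detection or coding by arm.
- Appetite, sleep and mild gastrointestinal symptoms stay self-reported.

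The cost is SAP wording, a code list, a check of the extract's fields and a few tables. No new participant contact is needed, and the sample size does not change.
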